## 10.6 INTERIM ANALYSES

A first interim analysis is planned for after completion of the 6 weeks visit in order to support the China NMPA registration. More specific details on the interim analyses will be included in the SAP.

## 11 SAMPLE SIZE JUSTIFICATION

Parratte et al.[51] looked at the effects of postoperative mechanical axis alignment on the survival of TKAs. They found that of the 398 TKAs reviewed in the paper there were 292 (73.4%) which post-operatively were defined as mechanically aligned (i.e. with a mechanical axis of  $0^\circ \pm 3^\circ$ ).

This study is designed to demonstrate superiority in the proportion of knees achieving post-operative leg alignment in the CORI Navigational group over the Conventional manual instrumentation group.

The proportion of mechanically aligned TKAs using NAVIO from a recent analysis was estimated to be 92.1% [52]. This proportion is expected to be equivalent if NAVIO was used to determine the proportion of mechanically aligned UKAs. Using these assumptions, enrollment of 63 UKAs per group will provide 80% power to show that the lower limit of the two-sided 95% confidence interval for the proportion of mechanically aligned UKAs is greater than that obtained from literature. To account for up to a 10% attrition rate in knees enrolled, 70 knees in each group (140 knees combined) will be enrolled into the randomized stage of the study. A minimum of an additional 5 subjects who will be treated with CORI directly to fulfil the learning needs of the surgeons will be enrolled at the pre-randomized study stage, thus leading to a minimum total study enrollment of 145 subjects.

## 12 ADVERSE EVENTS AND DEVICE DEFICIENCIES

### 12.1 DEFINITIONS

The categories of adverse events are shown in Table 12.1-12-1. The definitions for each of these categories are given in the subsequent sections.

**Table 12.1-12-1 Categories of Adverse Event**

	NOT DEVICE- RELATED	DEVICE- OR PROCEDURE-RELATED	
NON- SERIOUS	ADVERSE EVENT (AE)	ADVERSE DEVICE EFFECT (ADE)	
SERIOUS	SERIOUS ADVERSE EVENT (SAE)	SERIOUS ADVERSE DEVICE EFFECT (SADE) (SEE 12.1.3)	
		ANTICIPATED	UNANTICIPATED
		ANTICIPATED SERIOUS ADVERSE DEVICE EFFECT (ASADE)	UNANTICIPATED SERIOUS ADVERSE DEVICE EFFECT (USADE)

CONFIDENTIAL AND PROPRIETARY

This document contains information that is confidential and proprietary to Smith & Nephew PLC and Smith & Nephew, Inc. and is intended for use only by Smith+Nephew and its manufacturer. It shall not be reproduced or copied in whole or in part, nor shall the contents be disclosed by any means without prior written permission from Smith+Nephew, nor shall anyone make any use of it that is contrary to the expressed or implied wishes of Smith+Nephew.

TMP-CD-05-01 Clinical Protocol - Device - Revision D; SOP-CD-05 Clinical Protocol

Clinical Protocol	Study Number: CORI.2019.06
A Prospective, Multi-center, Randomized Controlled Study to Evaluate the Safety and Effectiveness of REAL INTELLIGENCE™ CORI™ in unicondylar knee arthroplasty (UKA) Procedure	Version: 4.0-Master, 07 Sep 2022
	Page: 87 of 167

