## 10.5 SAFETY ANALYSES

All safety analyses will be summarized separately for each of the groups (i.e. CORI Navigational and Conventional manual instrumentation groups) as follows:

- The number of adverse events will be reported by seriousness, relationship to study device and anticipation.
- The number of subjects experiencing adverse events will be summarised by seriousness, relationship to study device and anticipation.
- An overall AE summary table that will summarize as number (n) and percentages (%), the overall incidence according to subjects with at least one AE; subjects with at least one AE by worst severity (mild, moderate, or severe); subjects with at least one AE by worst outcome (resolved, ongoing/unresolved, or death); subjects with an AE that led to study discontinuation) and; subjects with at least one AE by worse relatedness to device. Other events such as SAEs, ADEs, SADEs or UADEs will also be similarly summarized using the number (n) and percentages (%).
- Incidence of device-related re-interventions that occur on-study will be summarized as number (n) and percentages as well as by type.
- A listing of device deficiencies that occur on-study will be provided.
- Knee implant revision rate will be summarized as proportions with 95% CIs estimated using exact binomial methods.

All safety endpoints will be summarized using the SAF analysis population.

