### 12.1.2 Adverse Device Effect

An Adverse Device Effect (ADE) is an adverse event related to the use of an investigational medical device.

Note 1: This definition includes adverse events resulting from insufficient or inadequate instructions for use, deployment, implantation, installation or operation, or any malfunction of the investigational medical device.

Note 2: This definition includes any event resulting from use error or from intentional misuse of the investigational medical device.

Note 3: This includes "comparator" if the comparator is a medical device.

**Not Related** - An AE is considered to be not related to the use of an IP or the procedure when the effect is DEFINITELY UNRELATED to have any relationship to the use of the IP or the procedure.

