#### CONFIDENTIAL AND PROPRIETARY

This document contains information that is confidential and proprietary to Smith & Nephew PLC and Smith & Nephew, Inc. and is intended for use only by Smith+Nephew and its manufacturer. It shall not be reproduced or copied in whole or in part, nor shall the contents be disclosed by any means without prior written permission from Smith+Nephew, nor shall anyone make any use of it that is contrary to the expressed or implied wishes of Smith+Nephew.

TMP-CD-05-01 Clinical Protocol - Device - Revision D; SOP-CD-05 Clinical Protocol

Clinical Protocol	Study Number: CORI.2019.06
A Prospective, Multi-center, Randomized Controlled Study to Evaluate the Safety and Effectiveness of REAL INTELLIGENCE™ CORI™ in unicondylar knee arthroplasty (UKA) Procedure	Version: 4.0-Master, 07 Sep 2022
	Page: 88 of 167

**Related** – An AE is considered to be related to the use of an IP or the procedure when there is a POSSIBLE, or DEFINITE relationship between the AE and the use of the IP or the procedure.

An ADE is further categorized depending on whether the criteria in section 12.1.3 and 12.1.4 are met.

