### **12.1.4 Anticipated/Unanticipated Serious Adverse Device Effect**

An Unanticipated Serious Adverse Device Effect (USADE) is a serious ADE which by its nature, incidence, severity or outcome has not been identified in the current version of the risk assessment.

Note 1: Anticipated serious adverse device effect (ASADE) is an effect which by its nature, incidence, severity or outcome has been identified in the risk assessment.

A list of potential ASADE for CORI is provided in Table 12.1.4-12-2. Please also refer to Section 4.4.5 Potential Adverse Effects.

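### A complication due to surgery but not to the device can be classed as AE/SAE or as ADE/SADE, because Table 12.1-12-1, the ADE definition and the relatedness rule in protocol Section 12.1.2 do not agree

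*Protocol*

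**What the plan says.** Protocol Section 12.1 presents Table 12.1-12-1 as the set of event categories and leaves their definitions to the sections that follow, so the two are meant to agree.

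- **Table 12.1-12-1.** One column is headed "NOT DEVICE- RELATED" and holds AE and SAE. The other is headed "DEVICE- OR PROCEDURE-RELATED" and holds ADE and SADE, with SADE split into ASADE and USADE.
- **Section 12.1.2, definition.** "An Adverse Device Effect (ADE) is an adverse event related to the use of an investigational medical device". A note extends this to the comparator if it is a medical device. The procedure is not mentioned.
- **Section 12.1.1.** Events related to the procedures involved are named in a note to the general AE definition. The ADE definition has no such note.
- **Section 12.1.2, relatedness rule.** An event counts as related "when there is a POSSIBLE, or DEFINITE relationship between the AE and the use of the IP or the procedure". The Not Related rule joins the same two causes.
- **Synopsis, Safety Data.** Relatedness to the device and to the surgical procedure are again given as alternatives in one judgement.
- **Section 12.3.** The investigator assesses each event's relationship to the device and to the procedure.
- **Section 10.5.** "The number of adverse events will be reported by seriousness, relationship to study device and anticipation". Subjects with events are summarised in the same way, and SAEs, ADEs, SADEs and UADEs as n (%), all by group. No row is planned for relationship to the procedure. (UADE is not in the abbreviation list; it is read here as USADE.)
- **SAP Sections 7.13 and 7.15.** Only a list of adverse events is produced, with no summary measures.

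**The concern.** Every subject in both arms has the same knee operation. If a possible link to that operation is enough to make an event an ADE or SADE, ordinary surgical complications enter the device-effect categories in both arms. If the definition sentence governs, the same events are plain AEs or SAEs. A site cannot tell from the text which applies, and two sites can differ without either breaching the protocol.

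Three things depend on the answer. The study is meant to support the safety of CORI for a registration, and the ADE, SADE and UADE rows in Section 10.5 are where a reader looks for device effects. Section 12.3 sets different reporting times for non-serious ADEs and other non-serious events. Section 8.1 allows the data to be combined with those of a parallel cohort study, which needs one ADE definition across both.

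**Working it through.** The question is one of definitions, so no figure in the plan needs reproducing. Take one test event: a complication judged possibly due to the operation and not due to CORI or to the comparator instruments.

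| Text applied | Class of the test event |
|---|---|
| Table 12.1-12-1, right-hand heading | ADE, or SADE if serious |
| Table 12.1-12-1, left-hand heading | AE, or SAE if serious |
| Section 12.1.2, ADE definition with comparator note | Not an ADE, so AE or SAE |
| Section 12.1.2, relatedness rule | Related, without saying to what |
| Synopsis, Safety Data | Related, without saying to what |

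Two conflicts follow. The table's columns are not mutually exclusive. Section 12.1.2 is also divided within itself, so changing the table heading alone would not settle the matter.

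**Effect on Section 10.5.** If sites follow the right-hand heading, the ADE, SADE and UADE rows take in procedure-only events. The rows by relationship to study device stay clean only if device relationship is recorded on its own. If the eCRF holds a single joined answer, as the relatedness rule would allow, those rows are affected too. The eCRF is not in the documents, so this cannot be settled.

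**Effect on reporting.** Section 12.3 gives SAEs and SADEs the same 24-hour limit, so a serious event is reported equally fast under either class. Non-serious events differ: ADEs have a prompt-reporting rule and other events follow routine timing.

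**Effect on USADE.** Only a serious event not identified in the risk assessment (Section 12.1.4) can become a USADE; identified ones become ASADEs.

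**Illustration with assumed rates.** None of these rates is in the documents. Let p be the percentage of subjects in each arm with a procedure-only event, and d the percentage added by CORI. Assume no overlap and no comparator-device events. The merged category gives p + d against p; a device-based category gives d against 0.

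- p = 20%, d = 5%: 25% against 20%, ratio 25/20 = 1.25, difference 5 points. Device effects are 5/25 = 20% of the CORI entries.
- p = 10%, d = 5%: 15% against 10%, ratio 15/10 = 1.5, difference 5 points. Device effects are 5/15 = 33% of the CORI entries.
- Device-based: 5% against 0%, difference 5 points.

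The difference is the same in all three, but its precision is not. With 70 per arm the simple standard error is √[(0.25×0.75 + 0.20×0.80)/70] = 7.0 points in the first case, √[(0.15×0.85 + 0.10×0.90)/70] = 5.6 points in the second, and √[0.05×0.95/70] = 2.6 points in the device-based case. That formula is crude when one arm has 0%, so this shows direction only.

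**The case against.** **The SAP has overtaken it.** The study stopped with four subjects (SAP Section 2) and no ADE, SADE or USADE counts will be produced. This stands. A reader might infer that the final safety results are distorted; the documents do not support that. What remains is the classification of events in the AE listing and the protocol text itself.

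**Section 12.1.2 does not simply contradict the table.** A reader might take the table as the lone error against a clear definition. That is too strong: the relatedness rule in the same section, and the synopsis, side with the table. The conflict is real but lies among three texts.

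**Device-specific information was already planned.** Section 12.3 asks about device and procedure. Section 10.5 tabulates by relationship to study device, summarises device-related re-interventions and lists device deficiencies. This limits the harm. It does not correct the ADE, SADE and UADE rows, and it works only if the two relationships are recorded separately.

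**Ordinary complications need not become USADEs.** A reader might infer that a post-operative pulmonary embolism, even in the conventional arm, would be a USADE because venous thromboembolism is named in neither Table 12.1.4-12-2 nor Section 4.4.5. This does not follow. Section 12.1.4 refers to the risk assessment, and Section 12.1.5 to the Investigator's Brochure and Risk Analysis Report, none of which is in the documents. The table offers only potential ASADEs, and includes infection, fracture, and nerve and vascular injury.

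**A broad category has merits.** The trial is non-blinded, so a device-only judgement is open to influence from knowledge of the arm. That is fair, and is a reason to show procedure-related events and all AEs by arm alongside it. It does not justify two conflicting rules.

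**Conclusion.** The inconsistency is real and wrong as written: a complication due to surgery alone has two possible classes, depending on which text a site follows. Under the protocol's planned analysis, the ADE, SADE and UADE rows could mix such events with device effects in both arms, and the tabulation by device relationship would offset this only in part.

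The size is unknown. A reader might conclude that ADE and SADE rates would mostly reflect the shared operation; that rests entirely on assumed rates such as the 20%, 10% and 5% used above. It also assumes no comparator-device events, although the comparator note to the ADE definition allows for them. For this study the practical effect is confined to how events are labelled and reported and to what the AE listing shows. The correction still matters for the protocol text and for any pooling with the parallel cohort study.

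**What to change.** 1. Reconcile the two headings of Table 12.1-12-1, the ADE sentence and the Related/Not Related rule in Section 12.1.2, and the synopsis wording, so that each event has one class.
2. Record relationship to device (investigational or comparator) and relationship to procedure as two separate eCRF judgements. Section 12.3 already calls for both assessments.
3. Base ADE, SADE, ASADE and USADE on the device judgement alone.
4. In Section 10.5, show procedure-related events separately by arm.
5. Under the current SAP, have the AE listing (Section 7.13) show both relationships for each event and state the rule that decided ADE/SADE status.

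Cost: some wording and at most one more field per event. There is one side effect to settle openly. Non-serious procedure-only events would no longer be ADEs, which changes the Section 12.3 timescale that applies to them; that timescale must be reconciled with the new classes. Section 12.5.1, which sets follow-up of ongoing events by a joined procedure-or-product relation, should be checked in the same pass.

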### 12.1.1 Adverse Event

An Adverse Event (AE) is any untoward medical occurrence, unintended disease or injury or untoward clinical signs (including abnormal laboratory findings) in subjects, users or other persons, whether or not related to the investigational medical device and whether anticipated or unanticipated.

Note 1: This definition includes events related to the investigational medical device or the comparator.

Note 2: This definition includes events related to the procedures involved.

Note 3: For users or other persons, this definition is restricted to events related to the use of investigational medical devices.

AE is used both to refer to AE which do not meet the definitions of Adverse Device Effects or Serious Adverse Events and as an umbrella term referring to adverse events of all classifications.

An AE can be any unfavorable and unintended sign (for example, an abnormal laboratory finding), symptom, or disease. For reporting purposes, emphasis is placed first and foremost on whether or not the event constitutes an untoward medical occurrence.

### 12.1.2 Adverse Device Effect

An Adverse Device Effect (ADE) is an adverse event related to the use of an investigational medical device.

Note 1: This definition includes adverse events resulting from insufficient or inadequate instructions for use, deployment, implantation, installation or operation, or any malfunction of the investigational medical device.

Note 2: This definition includes any event resulting from use error or from intentional misuse of the investigational medical device.

Note 3: This includes "comparator" if the comparator is a medical device.

**Not Related** - An AE is considered to be not related to the use of an IP or the procedure when the effect is DEFINITELY UNRELATED to have any relationship to the use of the IP or the procedure.

#### CONFIDENTIAL AND PROPRIETARY

This document contains information that is confidential and proprietary to Smith & Nephew PLC and Smith & Nephew, Inc. and is intended for use only by Smith+Nephew and its manufacturer. It shall not be reproduced or copied in whole or in part, nor shall the contents be disclosed by any means without prior written permission from Smith+Nephew, nor shall anyone make any use of it that is contrary to the expressed or implied wishes of Smith+Nephew.

TMP-CD-05-01 Clinical Protocol - Device - Revision D; SOP-CD-05 Clinical Protocol

Clinical Protocol	Study Number: CORI.2019.06
A Prospective, Multi-center, Randomized Controlled Study to Evaluate the Safety and Effectiveness of REAL INTELLIGENCE™ CORI™ in unicondylar knee arthroplasty (UKA) Procedure	Version: 4.0-Master, 07 Sep 2022
	Page: 88 of 167

**Related** – An AE is considered to be related to the use of an IP or the procedure when there is a POSSIBLE, or DEFINITE relationship between the AE and the use of the IP or the procedure.

An ADE is further categorized depending on whether the criteria in section 12.1.3 and 12.1.4 are met.

### **12.1.3 Related Serious Adverse Events and Serious Adverse Device Effects**

An AE or ADE is considered a **Serious** Adverse Event (SAE) or **Serious** Adverse Device Effects (SADE) if, it led to any of the following:

- a) Death,
- b) Serious deterioration in the health of the subject, users or other persons as defined by one or more of the following:
  - 1) A life-threatening illness or injury, or
  - 2) A permanent impairment of a body structure or a body function including chronic diseases, or
  - 3) In-patient or prolonged hospitalization, or
  - 4) -Medical or surgical intervention to prevent life-threatening illness or injury or permanent impairment to a body structure or a body function,
- c) Fetal distress, fetal death or a congenital abnormality or birth defect including physical or mental impairment

Note 1: Planned hospitalization for a pre-existing condition, or a procedure required by the study protocol, without serious deterioration in health, is not considered a serious adverse event.

### **12.1.4 Anticipated/Unanticipated Serious Adverse Device Effect**

An Unanticipated Serious Adverse Device Effect (USADE) is a serious ADE which by its nature, incidence, severity or outcome has not been identified in the current version of the risk assessment.

Note 1: Anticipated serious adverse device effect (ASADE) is an effect which by its nature, incidence, severity or outcome has been identified in the risk assessment.

A list of potential ASADE for CORI is provided in Table 12.1.4-12-2. Please also refer to Section 4.4.5 Potential Adverse Effects.

**Table 12.1.4-12-2 Potential Anticipated Serious Adverse Device Effects (ASADE)**

#	Potential Harm	Description
1	Allergic Reaction to Materials	Hypersensitivity caused by exposure to material constituents of the product that leads to local inflammatory reaction and tissue damage. Contact with an allergen may cause swelling and redness of the skin in minor cases. A severe anaphylactic reaction may occur.
2	Bone Fracture	Any break or fracture to any bone. (Applicable to displaced and non-displaced fractures)  The bone break could be reduced (set) and immobilized during the same surgery during which it occurred if it is detected. If the fracture occurs after the surgery, additional medical attention would be required. Subsequent healing returns normal body function for the subject.
3	Burn	3 rd degree burn extending through the dermis which requires excision. 4 th degree burn extending into the subcutaneous tissue, muscle and bone with eschar formation. Burns may be caused by thermal or chemical burns.
4	Cardiac Arrhythmia - symptomatic	Variation from the normal heart rhythm symptomatic.
5	Cement Leakage	Cement can end up in an unintended location in the joint. Cement leakage may cause early wear of poly or pain to the subject and may require revision surgery.
6	Unstable knee joint	The implant components are placed in such a way that there is too much laxity in the ligaments. The subject experiences instability throughout the range of motion, There is an increased risk of early loosening/ wear of the implant. This may impact the stability and wear of implant components.  Implants loosening could lead to early revision surgery.
7	Restricted Range of Motion	The implants are placed in such a way that excessive forces are placed on the ligaments (ACL, PCL, MCL, and LCL). This leads to an unintended reduction in the range of motion or progression of disease in a non- operative compartment. This may be serious, if the subject's range of motion has been worsened compared to the range of motion prior to surgery, or it has been restored sub- optimally.

## CONFIDENTIAL AND PROPRIETARY

This document contains information that is confidential and proprietary to Smith & Nephew PLC and Smith & Nephew, Inc. and is intended for use only by Smith+Nephew and its manufacturer. It shall not be reproduced or copied in whole or in part, nor shall the contents be disclosed by any means without prior written permission from Smith+Nephew, nor shall anyone make any use of it that is contrary to the expressed or implied wishes of Smith+Nephew.

Clinical Protocol	Study Number: CORI.2019.06
A Prospective, Multi-center, Randomized Controlled Study to Evaluate the Safety and Effectiveness of REAL INTELLIGENCE™ CORI™ in unicondylar knee arthroplasty (UKA) Procedure	Version: 4.0-Master, 07 Sep 2022
	Page: 90 of 167

#	Potential Harm	Description
8	Infection	
Invasion and multiplication of microorganisms in body tissues, especially microorganisms causing local cellular injury due to competitive metabolism, toxins, intracellular replication, or antigen-antibody response. The infection may lead to a diseased state in the receiving host if the host has inadequate resistance and/or lacks immunity to overcome the invasion by the pathogen.
 
Most typically, the resultant disease state can be treated through the use of antibiotics. When the pathogen is particularly virulent, or when the host has low resistance, the disease state may lead to a permanent impairment of some aspect of bodily function or, in extreme cases, to death. Infections caused by a transfer of body fluids during orthopedic surgery can in most cases be treated by a course of antibiotics. Severe infections that can occur by the transfer of body fluids during the procedure include HIV and hepatitis.

9	Delay	A delay in the operation time exceeding 60 minutes of intra-operative case time. A wound being open longer would more likely result in soft tissue edema, increased blood loss, muscle necrosis as a result of extended tourniquet time and a higher chance of infection.
10	Immature implant failure	Implant components wear before their intended service life resulting in early revision surgery.
11	Neurological Injury	Damage to the nerve systems of the subject's leg. A neurological injury could result in temporary or permanent paralysis.
12	Physical Injury - Serious	A physical injury that necessitates medical intervention.
13	Soft Tissue Damage	Damage to ligaments or tendons leading to loss of stability in the knee joint. In severe cases of ligament damage, additional surgery may be required.
14	Surgeon Operates on Wrong Part of Anatomy	The clinical impacts of operating on the wrong subject anatomy relate to the resultant function of the skeletal element that was treated and the need to repeat treatment for the desired skeletal element. The impact on the subject may be additional surgery under full anesthesia.
15	Vascular Injury - Main Low-extremity vessels	
Damage to the vascular systems of the subject's leg.
 
In severe cases, dis-vascularization occurs that is, the subject loses blood flow to the leg when a clot forms in significant arteries of the leg. Additional surgery would be required to correct blood

